5.5. KEY DEFINITIONS

Baseline is defined as last non-missing assessment prior to first dose. This definition will be used for all baseline and change from baseline analyses, unless specified otherwise.

5.6. MISSING DATA

Missing data will not be replaced. For quantitative assessments summarized by visit, summary statistics at each study visit will include data from subjects with non-missing values. Partial dates will be listed as recorded on CRF. No imputation of missing or

Statistical Analysis Plan

incomplete date/data will occur unless otherwise specified.

5.7. VISIT WINDOWS

There will be no derivation for visit windows in terms of summary of assessments. Nominal visits will be used for listings and tables.

6. DEMOGRAPHIC, OTHER BASELINE CHARACTERISTICS AND MEDICAL HISTORY

6.1. SUBJECT DISPOSITION

The following frequencies (number and percent) will be displayed by part and by treatment:

- Subjects enrolled (number only)
- Subjects who completed the study
- Subjects who discontinued early overall and by reason

The denominators for the percent calculations will be the number of subjects in safety set per treatment and combined, whether or not they are included in any of the analyses. No formal statistical comparison between the groups will be performed.

Subjects' completion/discontinuation status will be listed, including subject identifier, last visit/timewpoint, and the specific reason(s) for discontinuation.

All inclusion/exclusion criteria will be listed. Inclusion/exclusion criteria violations will be listed.

6.2. DEMOGRAPHICS, OTHER BASELINE CHARACTERISTICS

Demographic and baseline characteristics, will be summarized by means of descriptive statistics: continuous variables as mean, median, standard deviation, and interquartile ranges and categorical variables as frequencies and percentages, stratified by treatment arm based on the safety analysis set. Calculation of age is as follows:

- Age = (Informed Consent Date - Date of Birth + 1) / 365.25 and truncated to complete years.

6.3. MEDICAL HISTORY

A by-treatment summary table of the number and percentage of subjects by medical history system organ class (SOC) will be produced for subjects in the safety analysis set. Medical history will be sorted alphabetically by SOC using the Medical Dictionary for Regulatory Activities (MedDRA) coding dictionary, version 19.0. For the summary tables, a subject may appear more than once if he/she has more than one medical history coded under different SOC categories. However, the subject will be counted only once in the overall category. A by-subject listing with coded SOC and PT along with verbatim CRF term will also be provided.

6.4. PRIOR AND CONCOMITANT MEDICATION

Medications will be classified as prior if they were ongoing medications but stopped prior to the 1st dose of Study Treatment or concomitant (continued past or started on or after the first dose date of Study Treatment). Episodic medications (such as analgesics) will not be captured. The following rules will be applied to concomitant medications that were ongoing at the start of the trial, but discontinued during the clinical trial:

- If the stop date is completely missing, then it will be set to the last dose date;
- If the day is missing, then the last day of the month will be used. If this date is after the last dose date and the months are the same, then the last dose date will be used;
- If the day and month are missing, then the last day of the year will be used. If this date is after the last dose date and the years are the same, then the last dose date will be used.

All prior and concomitant medications will be classified using the Anatomical Therapeutic Chemical (ATC) classification codes and preferred drug names from the World Health Organization Drug Dictionary (WHO-DD), June 2016.

Summaries of prior and concomitant medications will be presented separately in tabular form using the second-level ATC term as an upper classification level and the preferred drug name as a lower classification level. All medications will be summarized by treatment group and sorted alphabetically by ATC level 2 and preferred drug name within a given ATC level 2 term. The summary will consist of the frequency and percent of safety subjects who used the medication at least once.

For each subject, the medication will be counted only once within a level-2 ATC and only once within a given preferred drug name level. A subject may appear more than once if he/she has more than one concomitant medication coded under different ATC categories; however, the subject will be counted only once in the overall category.

A by-subject listing with coded terms will also be provided along with calculated study day.

6.5. 12-LEAD ECG

An ECG will be performed at screening for all participants to determine eligibility. The ECG should include measurements of ventricular heart rate, PR, QRS, QT, QTc with assessment as to whether the ECG is normal or abnormal. Abnormal ECGs will be interpreted as clinically significant or not clinically significant.

A by-subject listing will be generated incorporating information and assessment results obtained from the designated central reading facility with provided investigator abnormality interpretations.

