6.2.2 Patient Identification Number and Group Assignments

Each participant who consents will be assigned a unique participant identification designation number (PID#), which identifies the participant for all study-related procedures that occur prior to receiving an allocation number. Once assigned, PID numbers cannot be reused for any reason. Information regarding participant's PID# and screen date will be documented on a screening log.

Study participants will be allocated to each of the two dosing groups such that the initial 5 eligible participants at each of the three study sites will be assigned to Group 1 at 1 mg/dose, the next 5 eligible participants at each study site will be assigned to Group 2 at 2 mg/dose. The final study participants will be allocated to the three study sites with 5 participants assigned to the 1 mg/dose group and allocated in a proportional manner between sites and the final 5 participants assigned to the 2 mg/dose group and similarly allocated in a proportional manner between study sites. Sponsor reserves the right to revise allocations between study sites should unexpected delays occur or any site cannot meet recruitment goals.

Medical History

Investigators should document all significant illnesses that the participant has experienced as Medical History. Illnesses' first occurring or detected during the study and/or worsening of an existing illness(es) that occur after the first vaccination are to be documented as AEs on the CRF. Prior treatments, defined as administered up to 8 weeks prior to the time of informed consent, will be recorded in the CRF as prior medications. Concomitant treatments, defined as continuing

or new treatments taken at or after the signing of the informed consent, will be recorded in the CRF as concomitant medications.

Travel History

Investigators should inquire as to travel to any country or region to include the South Pacific Islands, South America, Central America, or the Caribbean.

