6.3.1 Management of anxiety and pain due to EP procedure

Participants will be offered an analgesic (e.g. ibuprofen, acetaminophen) after injection/EP or EMLA cream before the procedure; the latter applied at least 15 min prior to vaccination.

Participants who are allergic to or have contraindications for use of ibuprofen or acetaminophen may be offered a suitable alternative.

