6.10 Concomitant medications and medical procedures

All medications taken or medical procedures performed within 8 weeks prior to enrollment and during the study that do not affect a participant’s eligibility for participation (see Section 4.3 - Exclusion Criteria) must be recorded on the CRFs. Dosage and frequency of immunosuppressive medications will also be recorded.

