3.9. STUDY PROCEDURES AND FLOWCHART

For an individual subject, study duration from screening through follow-up will be up to 1 year post final vaccination.

Statistical Analysis Plan

The below flowchart details the study procedure in Protocol 1.1:

Tests and Observations	Screen (Day -7 to -30)	Day0	Day1	Wk1 (±2d)	Wk4 (±5d)	Wk6 (±5d)	Wk12 (±5d)	Wk14 (±5d)	Wk20 (±10d)	Wk36 (±10d)	Wk60 (±10d) / Early termination
Clinical Assessments											
Consent	X										
Med history	X	X									
Demographics	X										
Travel hx ^a	X										
Medications ^b	X	X		X	X	X	X	X	X	X	
Phys Exam ^c	X	X		X	X	X	X	X	X	X	
Vital signs ^c	X	X		X	X	X	X	X	X	X	
Laboratory Assessments											
12-lead ECG	X										
CBC w/diff	X			X		X		X			
Chemistries ^d	X			X		X		X			
Serologies ^e	X										
Pregnancy ^f	X	X			X		X				
Serum ^g		X		X	X	X	X	X	X	X	
PBMCs ^g		X		X	X	X	X	X	X	X	
Blood Vol. per visit (mL)	15	70		80	70	80	70	80	70	70	70
Study Related Procedures											
Vaccine + EP		X			X		X				
EP Data ^h		X			X		X				
Memory aid ⁱ		X			X		X				
AEs		X	X ^j	X	X	X	X	X	X	X	X

Statistical Analysis Plan

- a Travel history to Central America, South America, Caribbean Islands, and South Pacific Islands at any time in past
- b Prior and concomitant, new medications will be recorded at all study visits (Day 0 through study discharge)
- c Full physical examination performed at screening and last visit or early termination only; perform targeted examinations at other visits as determined by Investigator or per participant complaints; record history of weight lifting or other significant physical activity; Vital signs will be performed pre and post vaccination at week 0, 4, and 12 week visits; height and weight will be recorded at screening.
- d Sodium (Na), potassium (K), chloride (Cl), bicarbonate (HCO3), glucose, BUN, Cr, ALT, AST, CPK
- e HIV antibody or rapid test, HBsAg, HCV antibody, dengue, West Nile, and chikungunya virus antibodies
- f Serum pregnancy test at screening and urine pregnancy test thereafter
- g Collect 4 tubes whole blood in ACD (yellow top) tubes for PBMCs; and 3 tubes of whole blood (red top) to obtain ~10 mL serum at the indicated time points
- h Download EP data within 48 hours of dose and transfer to GeneOne or its designee
- i Provide memory aid to study participants and review on next visit
- j Detail AEs assessed via telephone.

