* All tables (as data are available) are required for both the Interim (Week 14) and Final (Week 60) Analyses.

Statistical Analysis Plan

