10. INDEX OF LISTINGS

No.	Title	Population
16.2.1	Subject Disposition	ITT
16.2.2	Protocol Deviations	mITT
16.2.3.1	Demographics	Safety
16.2.3.2	Medical History	Safety
16.2.3.3	Prior/Concomitant Medications and Therapies	Safety
16.2.3.4	Travel History	Safety
16.2.5.1	Study Drug Administration	Safety
16.2.5.2	Investigational Device Information	Safety
16.2.7.1	Adverse Events	Safety
16.2.7.2	Serious Adverse Events	Safety
16.2.7.3	Adverse Events Leading to Study Discontinuation	Safety
16.2.7.4	Injection Related Treatment Emergent Adverse Events	Safety
16.2.7.5	Death	Safety
16.2.7.6	Injection Site Reactions	Safety
16.2.8.1	Laboratory Assessments –Hematology	Safety
16.2.8.2	Laboratory Assessments –Blood Chemistry	Safety
16.2.8.3	Laboratory Assessments –Serology	Safety
16.2.8.4	Pregnancy Test-Serum and Urine	Safety
16.2.9	Vital Signs	Safety
16.2.10	12-Lead ECG Results and Interpretations	Safety
16.2.11	Physical Examination	Safety
16.2.12.1.1	Zika Binding Antibody Titers by Subject	mITT
16.2.12.1.2	Zika Binding Antibody Titers by Subject	PP
16.2.12.1.3	Zika Binding Antibody Titers by Visit	mITT
16.2.12.1.4	Zika Binding Antibody Titers by Visit	PP
16.2.12.2.1	Neutralizing Antibody Titers against ZIKA Virus by Subject	mITT
16.2.12.2.2	Neutralizing Antibody Titers against ZIKA Virus by Subject	PP
16.2.12.2.3	Neutralizing Antibody Titers against ZIKA Virus by Visit	mITT
16.2.12.2.4	Neutralizing Antibody Titers against ZIKA Virus by Visit	PP
16.2.12.3.1	Antigen Specific Cellular Immune Responses by Subject	mITT
16.2.12.3.2	Antigen Specific Cellular Immune Responses by Subject	PP
16.2.12.3.3	Antigen Specific Cellular Immune Responses by Visit	mITT
16.2.12.3.4	Antigen Specific Cellular Immune Responses by Visit	PP

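### SAP 6.4 leaves analgesics out of the medication outputs, against the protocol's recording rules, and SAP 7.1 states no summary for the scheduled pain assessments after electroporation

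*SAP*

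**What the plan says.** **Medications.** SAP 6.4 separates prior from concomitant medications and then states "Episodic medications (such as analgesics) will not be captured". Later in the same section it states "All medications will be summarized by treatment group". Protocol 6.10 requires entry on the CRF of "All medications taken or medical procedures performed within 8 weeks prior to enrollment and during the study"; its only qualifier concerns items that affect eligibility. Under Medical History, Protocol 6.2.2 adds that continuing "or new treatments taken at or after the signing of the informed consent, will be recorded in the CRF as concomitant medications". Footnote b of the schedule, reproduced in SAP 3.9, has new medications recorded at every study visit. Protocol 6.3.1 says "Participants will be offered an analgesic (e.g. ibuprofen, acetaminophen) after injection/EP or EMLA cream before the procedure". The planned outputs are Table 14.1.4.1 (prior medications), Table 14.1.4.2 (concomitant medications) and Listing 16.2.3.3, "Prior/Concomitant Medications and Therapies". The footnote to the table index says "All tables (as data are available) are required for both the Interim (Week 14) and Final (Week 60) Analyses".

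**Pain.** SAP 3.10, item 2, names administration site pain alongside site reactions, up to 14 days after the final vaccination. Protocol 6.1.2.1 and SAP 3.4 both schedule a pain assessment at 0 and 30 minutes after EP. Protocol 6.6 lists pain as a CRF item apart from the five reaction components and refers the reader to Section 6.3.1. SAP 7.1 takes injection site reactions from the CRF in five categories: tenderness, pruritus, erythema, induration/swelling and bruising.

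**The concern.** The SAP states a rule for analgesics that the protocol does not contain. The protocol offers that drug class as part of the vaccination procedure, and Protocol 1.1.6 calls administration site pain the most significant finding with the device. The dose groups also differ in the number of injection/EP sites per vaccination (one against two), so analgesic use by dose group is something a reader of the safety results would look for. If the SAP is followed, the concomitant medication table would leave that use out without saying so.

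The pain issue is related but smaller. A component of a primary safety endpoint is measured at two fixed times after each vaccination, and the SAP does not say how those measurements are summarised.

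**Working it through.** No sample size or power figure is involved. The check is a comparison of text plus simple counts.

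1. **Recording rules against the SAP rule.** Protocol 6.10, Protocol 6.2.2 and footnote b contain no exception for analgesics or short-term use. SAP 6.4 contains one.

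2. **Two readings of *captured*.** If it means not collected, the SAP contradicts those three recording rules. If it means collected but not reported, the recording rules are not breached, but data recorded under them go unreported and the sentence is inconsistent with "All medications will be summarized by treatment group" in the same section. The sentence needs correcting on either reading.

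3. **Other routes for the data.** The memory aid (Appendix A) asks for medication taken since vaccination. Protocol 6.2.3.1 says memory aids are not collected and are not source documents. The CRF and the outputs built on it are therefore the reporting route.

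4. **Outputs affected.** SAP 6.4 treats as concomitant anything started on or after the first dose date. An analgesic or EMLA used around EP therefore belongs in Table 14.1.4.2. With two analyses, that is 1 table × 2 = 2 table deliveries, plus Listing 16.2.3.3. Table 14.1.4.1 is affected only for episodic medications stopped before the first dose.

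5. **Occasions.** 40 participants × 3 vaccinations = 120 planned vaccinations at which an analgesic or EMLA is offered. This counts offers, not use.

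6. **Pain in the planned outputs.** The index has 8 + 9 + 6 + 8 = 31 tables (14.1, 14.3.1, 14.3.2 and 14.4 series) and 6 + 2 + 6 + 4 + 3 + 12 = 33 listings. None is titled for pain. The nearest is Table 14.3.1.9, injection site reactions by visit, and the SAP 7.1 categories for those reactions omit pain. Pain recorded as an adverse event does enter the treatment-emergent tables (14.3.1.2 and related) and, where classed as injection related, Table 14.3.1.8 and Listing 16.2.7.4.

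7. **Number of scheduled pain assessments**, assuming full attendance:
   - Per participant: 20 × 3 × 2 = 120 in each group, 240 in total.
   - Per injection site, which is how Protocol 6.6 treats sites: Group 1, 20 × 3 × 1 × 2 = 120; Group 2, 20 × 3 × 2 × 2 = 240; total 360.

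8. **Scale.** Protocol 6.6 directs grading of administration site reactions by Appendix B, which has a pain row with Grades 1 to 4. The sentences that schedule the 0- and 30-minute assessments do not name a scale for them, and Section 6.3.1, to which Protocol 6.6 sends the reader for pain, contains none. One Appendix B criterion for Grade 2 (pain-reliever use over more than 24 hours) cannot be met at 0 or 30 minutes.

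**The case against.** The strongest reply is that little is lost. The investigator assigns severity grades (Protocol 7.1.5), so leaving analgesics out of a table changes no pain grade. Participants are observed for 30 minutes and any adverse event is recorded with its severity (Protocol 7.2). Memory aid entries of Grade 1 or higher must become adverse events (Protocol 6.2.3.1), and administration site events are summarised (SAP 5.3). The endpoint runs to 14 days and names no 0- or 30-minute value, so a time-point table is partly a matter of display. The SAP 6.4 sentence on summarising all medications can be read as a layout instruction. All of this stands, and it limits the point to reporting.

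It does not remove the conflict in SAP 6.4, which is with three separate recording rules as well as with that one sentence. Nor does it supply a summary for scheduled assessments that never become adverse event or site reaction records.

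A reader might go further than the documents allow in four ways:

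- **That pain has no scale.** Protocol 6.6 gives Appendix B as the general scale. What is missing is an express link to the two scheduled assessments. Appendix A is a take-home aid that staff regrade by Appendix B, and the visual analogue scale appears only in an abbreviation list, so neither is good evidence of a rival scale.
- **That the scoring unit is open.** Protocol 6.6 treats each injection site separately, and SAP 7.1 already counts injection sites.
- **That both medication tables lose the EP-related use.** By SAP 6.4's own definition, such use is concomitant.
- **That the 240 or 360 assessments are lost data.** The documents do not say how many would also be recorded as adverse events or site reactions.

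**Conclusion.** The concern holds on two counts, the first firmer than the second.

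(1) The episodic-medication sentence in SAP 6.4 conflicts with Protocol 6.10, Protocol 6.2.2 and footnote b, and is inconsistent with the section's own statement on summarising all medications. Its likely effect is the omission of analgesics, and possibly EMLA, from one table at two analyses and from one listing, for products offered at up to 120 vaccinations. EMLA is only possible because the SAP gives analgesics as an example and does not define episodic use.

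(2) SAP 7.1 omits pain from its injection site categories and states no summary for the 0- and 30-minute assessments, although primary endpoint 2 names pain. Pain as an adverse event is still reported.

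Neither count alters a pain grade or undermines the primary safety analysis. Both are worth correcting because the correction is nearly free. The conclusion assumes that the table and listing shells (SAP Attachments 1 and 2) and the Protocol Notification of 22 September 2016, which were not available, do not already deal with these points.

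**What to change.** 1. Delete the episodic-medication sentence from SAP 6.4. Analgesic and EMLA use recorded on the CRF then appears by dose group in the planned Table 14.1.4.2 and Listing 16.2.3.3, and episodic use that ended before the first dose appears in Table 14.1.4.1. If such use was not collected, deletion will not restore it, and the study report should state this as a limitation.

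2. Add pain to the SAP 7.1 categories and to Table 14.3.1.9, or add one descriptive table, by dose group, vaccination and time point. Count it per injection site, as in Protocol 6.6, and per participant. No between-group test is needed. If the shells already do this, cite them in SAP 7.1.

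3. State in the SAP which scale was used at 0 and 30 minutes, since the cross-reference in Protocol 6.6 leads to none.

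The cost is one deleted sentence, some coding of short-term medications, and one extended or added table. The downsides are slightly longer medication tables and some overlap between the pain display and the adverse event tables, which a footnote can explain.

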7. SAFETY ANALYSES

7.1. ADVERSE EVENTS

All AEs will be classified using MedDRA version 19.0.

Treatment-emergent AEs (TEAEs) will be defined as AEs onset or pre-existing conditions that worsen on/after the first study dose. Only TEAEs are included in the summaries and analyses, but all AEs, including non-treatment-emergent AEs will be presented in subject data listings. The following TEAEs will be summarized for each treatment group as follows:

- Number of TEAEs and number (%) of subjects with TEAEs by SOC and preferred term
- Number of TEAEs and number (%) of subjects with TEAEs by SOC, preferred term and severity (in hierarchical order: Potentially Life-threatening > severe > moderate > mild, missing severity will be considered as severe)
- Number of TEAEs and number (%) of subjects with TEAEs by SOC, preferred term and causality relationship to study drug (related vs unrelated)
- Number of TEAEs and number (%) of subjects with serious TEAEs by SOC and preferred term
- Number of TEAEs and number (%) of subjects with TEAEs leading to discontinuation of study drug by SOC and preferred term
- Number of Injection site reactions and number (%) of subjects as well as number (%) of injection sites with injection site reactions
- Deaths, if any, will be summarized, with reasons given

The summaries and analyses for TEAEs will be based on safety analysis set. TEAE will be summarized by proportions and exact 95% binomial CIs. The differences between the groups will be calculated in proportions. Fisher's Exact test will be used to evaluate the significance of the differences in frequency between groups.

Injection site reaction will be collected from CRF at the category of Tenderness, Pruritus, Erythema, Induration/Swelling and Bruising.

All AE summary tables including injection site reactions will only contain AEs within 14 days from the final vaccine administration.

Vital signs will be assessed at each visit starting from the screening visit. The by-visit summary table will include diastolic and systolic blood pressures, pulse, respiratory rate

Statistical Analysis Plan

and temperature. A by-subject listing will also be provided.

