9.6.1 Study Reporting Period of Adverse Events

All solicited and unsolicited adverse events will be collected throughout the study and recorded on the CRFs. The Study Report will analyze and summarize all adverse events throughout the study. Unsolicited AEs will be summarized for the 14 day period following each administration of Study Treatment. See next section for SAEs.

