9.7 Reporting of Medically Attended Adverse Events

MAAE will be collected during the entire study through one year following the last Study Treatment. As such, the reporting period for MAAE is the entire period following the signing of the informed consent form until study discharge.

A tabulation of all MAAE and their assessed relationship to Study Treatment will be included in all required periodic reports to regulatory agencies.

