2.2. TIMINGS OF ANALYSES

This SAP details the analysis of the study. The primary analysis of safety and tolerability is planned after all subjects complete the 14 week study visit corresponding to the completion of the Primary Study endpoint with a second analysis to correspond to when all have completed all study visits (either the final study visit or early termination from the study) to assess long-term safety and immunogenicity.

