3.2. SECONDARY OBJECTIVES

Secondary objectives are to evaluate:

- the safety to 1 year post vaccination of GLS-5700 in dengue virus-naïve adults
- the cellular and humoral response of GLS-5700 when delivered ID followed by EP in dengue virus-naïve adults

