3.4. STUDY DESIGN

This Phase I clinical trial will evaluate whether GLS-5700 administered via ID injection and followed by EP is safe, well-tolerated, able to generate an immune response against Zika virus in dengue virus-naïve participants, and whether the immune reactivity is dose-dependent. Injections will be given in the deltoid region followed immediately by EP with the CELLECTRA®-3P device.

GLS-5700 contains plasmid pGX7201 that encodes for a consensus sequence of the pre-membrane and envelope (prME) proteins of Zika virus.

Evaluation of ID administration of GLS-5700:

There are two arms for ZIKA-001. Participants (n=20 per group) will be administered GLS-5700 at one of two dose levels: 1 mg or 2 mg DNA/dose. Vaccine will be administered as 0.1 ml ID injections followed by EP with the CELLECTRA®-3P device. Participants will receive one (1 mg/dose) or two (2 mg/dose) injections into the deltoid region at vaccination at 0, 4, and 12 weeks (3 vaccination series).

Statistical Analysis Plan

Safety assessment: Participants will be monitored for adverse events utilizing the “Toxicity Grading Scale for Healthy Adult and Adolescent Volunteers Enrolled in Preventive Vaccine Clinical Trials” with labs assessed as per site normal values. Pain will be assessed immediately after EP and at 30 minutes post-EP. Laboratory safety assessments will be obtained at screening, 1 week following the 1st vaccination, and 2 weeks following the 2nd and 3rd vaccinations. Adverse events, including assessment of injection site reactions, will be monitored through 12 months after the final vaccination.

In the event that a stopping criterion is reached, the study will not continue until a full discussion has been conducted with the Medical Monitor, Principal Investigator, and Institutional Review Board (IRB)/Research Ethics Board (REB) (if applicable).

- One third (1/3) or more participants experience an ERER assessed as related to Study Treatment;
- Three or more participants in the same treatment arm discontinue due to an AE related to the Study Treatment;
- Any participant experiences a potentially life threatening AE, Grade 4 AE or death assessed as related to Study Treatment;
- Two or more participants within a treatment arm experience the same or similar grade 3 or 4 adverse event, assessed as related to Study Treatment;

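### The SAP confines every AE summary table, at the final analysis too, to events within 14 days of the last vaccination, so the 1-year safety objective has no AE summary

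*SAP*

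**What the plan says.** SAP 7.1 sets one rule for all adverse event tables: "All AE summary tables including injection site reactions will only contain AEs within 14 days from the final vaccine administration". It makes no exception for the final analysis. The footnote to SAP 9 then says: "All tables (as data are available) are required for both the Interim (Week 14) and Final (Week 60) Analyses". The index contains a single set of AE tables, 14.3.1.1 to 14.3.1.9, and none is labelled for the period to Week 60.

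Elsewhere the documents commit to more:

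- SAP 3.2 makes "the safety to 1 year post vaccination of GLS-5700 in dengue virus-naïve adults" a secondary objective.
- SAP 2.2 says the second analysis, after all study visits, is "to assess long-term safety and immunogenicity".
- SAP 3.4: "Adverse events, including assessment of injection site reactions, will be monitored through 12 months after the final vaccination".
- Protocol 9.6.1: "The Study Report will analyze and summarize all adverse events throughout the study".
- Protocol 9.7: "MAAE will be collected during the entire study through one year following the last Study Treatment". The SAP indexes name neither a table nor a listing for these events.

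Protocol 8.3.1 also uses 14 days, but only for what it calls the main summary, and there (as in 9.6.1 for unsolicited events) the window follows each administration, not just the last.

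**The concern.** The 14-day limit comes from the primary endpoint (Protocol 2.2, SAP 3.10). SAP 7.1 extends it to every AE table. The Week 60 tables of TEAEs, Grade 3+ TEAEs, related TEAEs and serious TEAEs would then hold only events that were already eligible at Week 14.

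This is a first-in-human study (Protocol 1.1.5), and Protocol Table 1.4 lists autoimmune disease among the risks of unknown or theoretical frequency. Long follow-up exists to look for events of that kind. A serious event at Month 8 would be missing from Table 14.3.1.6 and would appear only in a by-subject listing. A reader of a Week 60 table showing no serious events could take it to mean that none occurred during the year of follow-up.

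**Working it through.** **Inputs.** Vaccinations at Weeks 0, 4 and 12 and the last visit at Week 60 (SAP 3.8 and 3.9); 14-day limit after the final vaccination (SAP 7.1); N = 40 (SAP 3.6). The limit is read as covering first dose through 14 days after the last dose. Nominal visit days are used.

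**Step 1: does another table fill the gap?**

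| Source | Covers AEs after Week 14? |
|---|---|
| Tables 14.3.1.1 to 14.3.1.9 | No, limited by SAP 7.1 |
| Analysis-set grid (SAP 4), secondary endpoints (SAP 3.11) | No long-term safety entry |
| Laboratory tables | No, safety laboratory tests end at Week 14 |
| Vital signs by visit (SAP 7.1, 7.4) | May run past Week 14, but do not summarise AEs and are not in the table index |
| Listings 16.2.7.1, 16.2.7.2, 16.2.7.5 | Yes, but as individual records only |

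**Step 2: follow-up inside and outside the window.**

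- Window closes: 12 × 7 + 14 = Day 98.
- Follow-up ends: 60 × 7 = Day 420.
- Outside the window: 420 − 98 = 322 days; 322 / 420 = 76.7%.
- Of the 48 weeks after the last dose: (48 − 2) / 48 = 95.8% lies outside.
- Participant-time outside, if all 40 complete: 40 × 322 / 365.25 = 35.3 participant-years.

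**Step 3: SAP window against the protocol's per-dose window.** Three windows of 14 days give 3 × 14 = 42 days. The SAP's continuous window is 98 days, and 98 / 42 = 2.3. The main safety summaries in the two documents therefore differ 2.3-fold in time at risk.

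**Step 4: effect on the stated detection probability.** SAP 3.6 gives 80% for at least one event at 4% incidence. Check: 1 − (1 − 0.04)^40 = 0.8046, which agrees.

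For illustration, treat the incidence as a 60-week figure and assume a constant hazard (neither is in the documents). The 14-week risk is 1 − (1 − q)^(14/60). For q = 4% this is 0.95%, and the chance that an AE table shows at least one event in 40 is 1 − (1 − 0.0095)^40 = 31.7%.

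| 60-week incidence | At least one event in a table, limit as written | Tables to Week 60 |
|---|---|---|
| 2% | 17.2% | 55.4% |
| 4% | 31.7% | 80.5% |
| 5% | 38.0% | 87.1% |
| 10% | 62.6% | 98.5% |

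An event that arises only after Day 98 has no chance of entering an AE table.

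**The case against.** The strongest reply is that the SAP conflicts with itself rather than dropping the objective. SAP 5.3 promises summaries of serious AEs and of Grade 3+ TEAEs with exact intervals and Fisher's test, and states no time limit. The TEAE definition has no end date, and SAP 2.2 gives the second analysis to long-term safety. But SAP 5.3 sets no window of its own and defines no 1-year table, so its summaries fall under the rule in 7.1 for all AE tables. No passage overrides that rule. If the reading is disputed, the text still needs reconciling.

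A second reply is that with 40 participants the listings show every late serious event and death individually, and that the study is descriptive and, by Protocol 8.4, underpowered for comparing arms. That lowers the practical loss, but Protocol 9.6.1 promises analysis and summary, and a listing provides neither.

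Several points stand and narrow the illustration:

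- Protocol 9.6.1 itself uses a 14-day window after each dose for unsolicited events, narrower than the SAP's. It sits beside the whole-study commitment and does not replace it.
- Protocol 9.7 requires medically attended events to be tabulated in periodic regulatory reports. The gap is in the SAP's tables for the study report.
- Table 14.3.1.7 concerns discontinuation of study drug. Dosing ends at Week 12, so it loses little or nothing.
- Reactogenicity clusters early, so the share of events left out need not equal the share of time.
- The table shells and the September 2016 protocol notification were not available. A shell footnote could state a different window, but the SAP text does not.

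**Conclusion.** The concern holds, and the plan is wrong as written. SAP 7.1 and the index footnote together leave 46 of 60 study weeks (76.7%), and 46 of the 48 weeks after the last dose, outside every AE summary table. The secondary objective of safety to 1 year would have listings but no AE proportion, interval or comparison by dose. This conclusion rests on the text and the nominal schedule alone. The figure of about 35 participant-years assumes full completion. Reading 77% as a share of unsolicited events, and the detection probabilities in the working, needs a constant event rate and is illustrative only. The primary endpoint is unaffected and no data are lost. It should be corrected before the final analysis, because a stated rule would keep late serious events out of the final tables.

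**What to change.** Replace the sentence in SAP 7.1 with wording such as:

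> Primary safety tables include TEAEs from first dose through 14 days after the final vaccination. For the final analysis, Tables 14.3.1.1 to 14.3.1.9 are repeated for all TEAEs and injection site reactions from first dose through Week 60. SAEs, deaths and MAAEs are tabulated over the whole study.

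Table 14.3.1.9 is included because SAP 3.4 has injection site reactions monitored for 12 months after the last dose. Then:

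- add a medically attended AE table and listing to the SAP indexes;
- state the window in each table title and in the index footnote;
- add 1-year safety to the analysis-set grid in SAP 4;
- align Protocol 8.3.1 and 9.6.1 with the primary window in Protocol 2.2, or label the per-dose summary as a separate table.

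The cost is SAP wording, a protocol clarification, one repeat run of existing shells, and the new table and listing. No new data collection is needed.
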